3.3 Subject Data and Study Conduct

3.3.1 *Participant Disposition*

Counts and percentages of subjects who were randomized, completed the treatment period, discontinued treatment (including primary reason for discontinuation), completed the study, and prematurely discontinued from the study (including primary reason for discontinuation) will be summarized by treatment group and overall.

For each scheduled visit, counts and percentages of subjects who did not complete the visit, partially completed the visit in-person, or completed the visit via virtual method will be summarized by treatment group and overall. The denominator for calculating percentages will be based on the number of randomized participants.

Participants disposition and exclusion and inclusion criteria violations will be listed.

3.3.2 *Protocol Deviations*

Protocol deviations will be identified based on clinical data as defined in the Protocol Deviation Plan, where all protocol deviations will be defined as either CSR reportable or non-CSR reportable deviations. The CSR reportable protocol deviations will be categorized and separated by treatment group. The CSR reportable deviations will include all randomized subjects using counts and percentages.

A listing of CSR-reportable protocol deviations will be generated.

3.3.3 *Analysis Populations*

Counts and percentages of subjects in each analysis population will be summarized by treatment group and in total based on all randomized subjects. Reasons for exclusion from PP Population will also be summarized.

3.3.4 *Demographic and Baseline Characteristics*

The following demographic and baseline characteristics will be summarized with descriptive statistics or counts and percentages of subjects as appropriate by treatment group and overall, for the ITT Population:

- Age and age categories (<65 years, 65 to 74 years, and 75+ years)
- Sex
- Race
- Ethnicity
- Height
- Weight
- Body Mass Index (BMI)
- Region (Asia, Eastern Europe, Western Europe and North America)
- Country (USA, Japan, China, Other)
- Diabetes (yes, no)
- HDL-C (<40mg/dL, 40 - <60 mg/dL, ≥60mg/dL)
- ApoB (<60mg/dL, 60 - <90 mg/dL, ≥90mg/dL)
- ApoA1 (<110 mg/dL, ≥110 and <125 mg/dL, ≥125mg/dL)
- Lipoprotein(a) (<75nmol/L, ≥75 and <125 nmol/L, ≥125nmol/L)
- Non-HDL-C (<100 mg/dL, ≥100 and <130 mg/dL, ≥130mg/dL)
- LDL-C (<70mg/dL, ≥70 and <100 mg/dL, ≥100mg/dL)
- TG (<150 mg/dL, ≥150mg/dL)
- HbA1c (<5.7%, ≥5.7 to ≤6.4%, >6.4%)
- Urinary albumin:creatinine ratio (normal, micro-albuminuria, macro-albuminuria)
- eGFR (<30ml/min/1.73 m², ≥30 to <45ml/min/1.73 m², ≥45 to <60ml/min/1.73 m², ≥60 to <90ml/min/1.73 m², ≥90ml/min/1.73 m²)
- Statin treatment (high dose, low or moderate dose, none). High dose statin will be defined as atorvastatin 40 or 80 mg, rosuvastatin 20 or 40 mg. Participants will be defined as having high dose statin based on the data collected in the eCRF and if any following were used at baseline: average daily dose of atorvastatin ≥40 mg or average daily dose of rosuvastatin of ≥20 mg. For Japan only, high dose statin includes atorvastatin 10 or 20 mg for non-familial hypercholesterolemia, atorvastatin 20 or 40 mg for heterozygous

familial hypercholesterolemia, rosuvastatin 10 or 20 mg. Participants will be defined as having high dose statin treatment, for Japan only, if any following were used at baseline: average daily dose of atorvastatin ≥ 10 mg or average daily dose of rosuvastatin of ≥ 10 mg. Participants having other doses of statin or other statin treatment will be defined as low or moderate.

- Ezetimibe use (yes, no)
- Glucose-like peptide-1 (GLP1) use (yes, no)
- Sodium-glucose co-transporter-2 (SGLT2) use (yes, no)
- A high-sensitivity C-reactive protein [hs-CRP] (<2 mg/dL, ≥ 2 mg/dL)
- HeFH (yes, no)
- HIS, non-HIS
- HeFH (Genotyping confirmed or DLCN>8 points or Simon Broome definite); Simon Broome possible Familial Hypercholesterolemia (FH) diagnosis.

If they differ from the ITT Population, summaries will also be provided for the FAS, the mITT Population, mITT On-Treatment Population, the PP Population, and the Safety Population. Demographic characteristics data will be provided in participants listings.

3.3.5 Medical History

Medical history will be coded to system organ class and preferred term using the current Medical Dictionary for Regulatory Activities (MedDRA) version. Counts and percentages of subjects with medical history by system organ class (SOC) and preferred term (PT) will be summarized by treatment group and in total based on all randomized subjects.

A listing of all medical history data will be provided.

3.3.6 Concomitant Medications

The Prior & Concomitant Medications case report form where medication start and stop dates are recorded, will be used to determine whether the medications are prior or concomitant to the study treatment. Concomitant medications are defined as those used on or after the first dose of the study drug. Prior medications are defined as those used prior to and stopped before the first dose of study drug. All prior and concomitant medications will be coded using the current World Health Organization (WHO) Drug Dictionary. Counts and percentages of participants taking prior and concomitant medications will be summarized by anatomical therapeutic chemical (ATC) class and preferred term by treatment group and overall, for the Safety Population.

Concomitant medications will be listed.

3.3.7 Study Drug Exposure and Compliance

Subjects' exposure to randomized study drug will be summarized with descriptive statistics for the Safety and mITT On-Treatment Populations. Days of exposure to study drug will be calculated as

$$\text{date of last dose of study drug} - \text{date of first dose of study drug} + 1.$$

For subjects whose date of first dose from the initial bottle dispensed was not available, the date of randomization will be used to assign the date of first dose. For subjects who failed to provide the date of last dose of study drug, the earliest date between the end of treatment date and the date of the end of study/early termination will be used.

Days of exposure to study drug will be summarized by treatment group based on the Safety Population with counts and percentages of subjects with exposure in the following categories:

- <3 weeks
- 3 – <5 weeks
- 5 – <7 weeks
- 7 – <9 weeks
- 9 – <11 weeks
- 11 – <13 weeks
- 13 – <19 weeks
- 19 – <25 weeks
- 25 – <28 weeks
- 28 – <34 weeks
- 34 – <40 weeks
- 40 – <50 weeks
- 50 – <54 weeks
- >=54 weeks

The percentage overall compliance to study drug will be calculated using the following formula:

$$\frac{\# \text{ tablets dispensed} - \# \text{ tablets returned}}{\# \text{ expected dosing days}} \times 100$$

If study drug is not returned, the number of tablets returned and lost will be considered 0 for the compliance calculation. The expected dosing days will be calculated as the earliest date between the end of treatment date and the date of early termination – the date of randomization – any missed doses+1 (*missed doses defined as number of doses missed during IP interruptions due to AE or IP interruptions that are longer than 14 days*).

Percent compliance to the study drug regimen will be summarized by treatment group and in total based on the Safety Population with descriptive statistics and with counts and percentages of subjects with compliance in the following categories:

- <80%
- 80% to 120%
- >120%

Study drug interruptions due to AE or IP interruptions longer than 14 days will be listed.

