## 5.5.2 Study Drug Preparation and Dispensing

Participants will receive one 40-count bottle of study drug at Visit 2, two 40-count bottles at Visit 3, and three 40-count bottles at Visits 4, 5, and 6. Study drug will be assigned in a double-blind manner via the IRT system at each applicable study visit.

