2.2 Study Design

2.2.1 Overview

This study is a multisite, placebo-controlled, double-blind, randomized Phase 3 study to evaluate the efficacy, safety, and tolerability of obicetrapib in participants with underlying HeFH and/or a history of ASCVD who are not adequately controlled by their lipid-modifying therapy.

Approximately 2400 eligible participants will be randomized in a 2:1 ratio, respectively, to the following treatment groups:

- Obicetrapib group: one 10 mg obicetrapib tablet once daily; or
- Placebo group: 1 placebo tablet once daily.

Treatment allocation will be stratified based on CV risk (HeFH or non-HeFH) and Baseline statin dose (high-intensity statins [HIS] or non-HIS). At least 70% of the participants enrolled into this study must be taking HISs. Participants with underlying HeFH but without a history of ASCVD will comprise up to a maximum of 20% of the total participants enrolled into the study. Starting on Day 1, each participant will self-administer their assigned study drug once daily until Day 365. During the Treatment Period, participants will return to the study site for efficacy and safety assessments. Blood samples for pharmacokinetic (PK) assessment will be collected at specified visits throughout the study. Participants will return to the site for the End Of Study (EOS) Visit (Visit 8) approximately 35 days after last dose of study drug for safety assessments.

A subset of approximately 200 participants from selected study sites who consent to participate will be enrolled in an ambulatory blood pressure monitoring (ABPM) substudy. These participants will have a 24-hour ABPM assessment conducted at Screening (Visit 1) and Visit 6 (Day 270). In order to participate in the substudy, participants must provide written informed consent in a substudy-specific informed consent form (ICF) and must be able to provide an acceptable 24-hour ABPM data collection at Screening (Visit 1).

The study drug blind will be maintained through the EOS Visit (Visit 8). Participants, the Sponsor, Investigators, and all study site personnel involved in the study, including personnel carrying out study procedures, evaluating participants, entering study data, and/or evaluating study data, will

remain blinded to treatment allocations until all participants have completed the EOS Visit assessments and the database has been locked for analysis.

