3.2.2 The Full Analysis Set (FAS)

The FAS will include all participants who are randomized into the study, take any study drug, and have at least 1 post-treatment lipid data assessment. Treatment classification will be based on the randomized treatment.

3.2.3 *Modified Intent-to-Treat (mITT) Population*

The mITT Population will include all randomized participants who receive at least 1 dose of any study drug and have data for both the Day 1 and Day 84 LDL-C assessments. Treatment classification will be based on the randomized treatment.

3.2.4 *Modified Intent-to-Treat (mITT) On-Treatment Population*

The mITT On-Treatment Population will include all randomized participants who, have data for both the Day 1 and Day 84 LDL-C assessments. Participants in the obicetrapib group with PK values less than 3 standard deviations from the mean obicetrapib concentration should be excluded. Treatment classification will be based on the randomized treatment.

Rationale: in previous studies, such as ROSE (protocol number TA-8995-201) and TULIP (protocol number TA-8995-03), and ROSE2 (protocol number TA-8995-202), it was demonstrated that the minimally observed obicetrapib concentration for C_{max} was less than three standard deviations from the mean at respectively Week 4 and Week 12 [3-5].

3.2.5 *Per-Protocol (PP) Population*

The PP Population will include all participants in the mITT Population who did not experience a major protocol deviation that potentially impacted the primary efficacy endpoint. The PP Population, along with the reason for exclusion, will be finalized prior to study unblinding.

3.2.6 *Safety Population*

The Safety Population will include all participants who receive at least 1 dose of any study drug. Treatment classification will be based on the actual treatment received. The Safety Population will be the primary population used for the safety analyses.

3.2.7 *24-hours ABPM Population*

The 24-hour ABPM Population will include all participants in the ITT Population who received at least 1 dose of any study drug and have valid data for both the baseline and Day 270 24-hour ABPM assessments and have 80% to 120% treatment compliance.

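### The compliance score that selects the primary ABPM Population counts unreturned drug as taken and covers the wrong period

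*SAP*

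**What the plan says.** Both documents define compliance as tablets dispensed minus tablets returned, divided by expected dosing days (Protocol 5.5.4; SAP 3.3.7). The SAP adds two rules that the protocol does not have.

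- Numerator: "If study drug is not returned, the number of tablets returned and lost will be considered 0 for the compliance calculation".
- Denominator: "The expected dosing days will be calculated as the earliest date between the end of treatment date and the date of early termination", minus the randomization date, minus missed doses, plus 1. The missed doses taken out are "missed doses defined as number of doses missed during IP interruptions due to AE or IP interruptions that are longer than 14 days".

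SAP 3.3.7 calls the result overall compliance. It is the only compliance definition in the SAP.

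SAP 3.2.7 requires members of the 24-hour ABPM Population to "have valid data for both the baseline and Day 270 24-hour ABPM assessments and have 80% to 120% treatment compliance". SAP 3.5.7 makes that population primary for the 3 mmHg non-inferiority test. Protocol 9.2.6.1 asks only for an acceptable Screening recording, and SAP Section 6 does not list the compliance condition as a change.

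Dispensing under Protocol 5.5.2 is "one 40-count bottle of study drug at Visit 2, two 40-count bottles at Visit 3, and three 40-count bottles at Visits 4, 5, and 6".

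**The concern.** A tablet count that only fed a descriptive table could tolerate crude rules. This one decides who enters the primary analysis of a safety question, and it can go wrong in three ways.

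- More tablets are dispensed than there are days, so counting unreturned drug as taken can push a fully adherent participant above 120%.
- The score runs to the end of treatment but selects people for a Day 270 comparison, so intake after the measurement can decide membership.
- Taking certain interruptions out of the denominator lets a participant with a long gap score as fully compliant. That may be acceptable as a measure of adherence. A pressor-effect analysis, however, depends on exposure.

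At stake are the power of a substudy of about 200 participants and, possibly, dilution of a real blood-pressure effect.

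**Working it through.** **The plan's own figure.** SAP 2.2.2 gives about 200 participants, margin 3 mmHg, true difference 0, SD 8 and 1-sided 0.05; allocation is 2:1.

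- SE = 8 × √(1/66.7 + 1/133.3) = 1.20 mmHg.
- Power at 1-sided 0.05 = Φ(3/1.20 − 1.645) = 80.4%. The stated figure of more than 80% is reproduced, with almost nothing to spare.
- At the 1-sided 0.025 in SAP 3.5.7: Φ(2.50 − 1.96) = 70.5%. The mismatch in level is a separate matter, but it sets the power actually available.
- Assumed losses of 5%, 10% and 20% of those analysed give 78.6%, 76.6% and 72.3% at 0.05, and 68.3%, 66.0% and 60.9% at 0.025.

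**Nothing returned.**

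- Dispensed: 40 + 80 + 120 + 120 + 120 = 480 tablets.
- Score at Day 365: 480/365 = 131.5%, whatever was taken.
- Across the ±7-day window: 480/358 = 134.1% to 480/372 = 129.0%. The score reaches 120% only at 480/1.2 = 400 days.
- Stopping the count at Day 270 does not cure this alone: 360/270 = 133.3%.

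**Wrong period** (all bottles returned, visits on schedule).

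- 100% of doses to Day 270, then 20% of the last 95: (270 + 19)/365 = 79.2%, excluded although exposure up to the measurement was complete.
- 75% to Day 270, then 100%: (202.5 + 95)/365 = 81.5%, included although exposure up to the measurement was below the band.

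**Interruption days removed** (all bottles returned, every other dose taken).

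- A 120-day AE interruption, or one of that length for any reason: score 245/(365 − 120) = 100%; coverage 245/365 = 67.1%.
- Coverage first falls below 80% at 74 days: 291/365 = 79.7%. The score is still 100%.
- Non-AE interruptions of 14 days or less stay in the denominator.

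**Illustration of dilution.** Assume a true on-drug effect of exactly 3 mmHg and 200 analysed. If 10% of the analysed obicetrapib arm had no drug effect at Day 270, the mean difference is 2.7 mmHg and the chance of declaring non-inferiority is Φ(0.3/1.20 − 1.96) = 4.4% instead of 2.5%. At 20% it is Φ(0.6/1.20 − 1.96) = 7.2%. If those participants instead kept 70% of the effect, the differences are 2.91 and 2.82 mmHg and the figures about 3.0% and 3.5%. None of these shares comes from the documents.

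**The case against.** The strongest reply is that the SAP already surrounds the primary ABPM analysis with others. The sensitivity analysis in SAP 3.5.7 has no compliance condition, so the adherent participant who returns nothing is back in. The supplemental analysis there leaves out anyone who discontinued study drug before Day 270. Longer and AE-related interruptions are listed, and Protocol 5.5.4 asks sites to clarify tablet discrepancies. No LDL-C analysis population explicitly uses the score. All of this stands and limits the consequence. It does not repair the primary set: the sensitivity analysis does not decide non-inferiority, and the supplemental analysis stays inside the gated set and, as worded, does not address temporary interruptions.

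It is also fair that excusing AE interruptions is a usable definition of adherence. Counting those days as missed under the same 80% limit could remove people whose drug was interrupted because of raised blood pressure. That would be an outcome-related exclusion and could itself favour non-inferiority.

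A reader might infer more than the text supports:

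- That poor takers enter through unreturned bottles. A 70% taker who keeps only the last three bottles would score (0.7 × 270 + 120)/365 = 84.7%, but only if the non-return rule works dispensing by dispensing. If it applies only when nothing comes back, it causes false exclusion alone.
- That anyone who stops early scores about 100%. This needs the end of treatment date to mean the last dose. It may mean the visit date, and Protocol 4.3 keeps people who stop drug in scheduled visits.
- That false exclusion favours non-inferiority. The same rule applies to both blinded arms; the demonstrated effect is lost power.

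**Conclusion.** The point holds as a defect in how the primary ABPM set is selected. Three results follow from the text, reading the condition in SAP 3.2.7 through the only compliance definition the SAP gives: non-return of all drug means a score of 129% to 134% and exclusion regardless of intake; intake after Day 270 can move a participant across the 80% limit; and an excused interruption can turn 67% coverage into 100%.

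The loss of power is the firmest consequence, because the design has 80.4% at best under its planning level and 70.5% under its analysis level. How many participants would be lost is not known.

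A reader might go further and conclude that the formula raises the type I error to 4.4% or 7.2%. The documents do not support that as a finding. They give no rate of interruption or non-return, those figures assign the affected participants no drug effect at Day 270, and a 120-day gap could end well before that visit or fall partly after it. Dilution is possible; its size is unknown.

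**What to change.** In the SAP:

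1. Treat unreturned bottles as unknown: drop them and their dosing interval from both numerator and denominator. Up to three bottles are dispensed together, so the interval between visits is the natural unit.
2. State that nobody leaves the 24-hour ABPM Population only because drug was not returned. Someone who returns nothing then has unknown compliance and stays in, which also settles the 0/0 that step 1 would otherwise produce.
3. For the ABPM condition, compute compliance from Day 1 to the Day 270 assessment. Bottles are returned at Visit 6, so no new data are needed.
4. Do not tighten the condition by counting interruption days as missed. Report coverage with those days kept in the denominator beside the current figure.
5. Extend the supplemental analysis in SAP 3.5.7 to leave out participants whose study drug was interrupted at the Day 270 assessment, and read it together with the ungated sensitivity analysis.
6. Define the end of treatment date, and say whether non-return applies per bottle, per dispensing or only when nothing is returned.

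The cost is SAP wording, reprogramming, and some participants whose compliance is partly unknown.

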3.4 Efficacy Assessment

The ITT Population will be the primary population for the efficacy analysis. Efficacy will also be analyzed using the FAS, mITT Population, mITT On-Treatment Population, and PP Population as supportive analyses.

3.4.1 Primary Efficacy Endpoints

Primary Analysis

The primary efficacy endpoint is the percentage change from Baseline to Day 84 in LDL-C in the obicetrapib group compared to placebo group.

The LDL-C values measured by preparative ultracentrifugation (PUC) will be used. If the later is not available, the LDL-C values will be assumed missing.

All the analysis for primary efficacy endpoint will be repeated with LDL-C values calculated as follows:

1. LDL-C will be calculated using the Friedewald equation unless triglycerides ≥ 400 mg/dL or LDL-C ≤ 50 mg/dL; where, LDL-C level will be measured directly by PUC.
2. LDL-C will be calculated using the Martin-Hopkins equation unless triglycerides ≥ 400 mg/dL or LDL-C ≤ 50 mg/dL; where, LDL-C level will be measured directly by PUC.

Primary Estimand

To assess the primary efficacy endpoint, the primary estimand is defined by the following key attributes:

- **Treatment:** obicetrapib versus placebo
- **Target Population:** participants who are randomized into the study
- **Analysis Population:** The ITT Population
- **Intercurrent events:** treatment discontinuation, prohibited medication use
- **Analysis set and handling of intercurrent events:** Treatment policy strategy will be used. All available values of LDL-C at Baseline and Day 84 will be included in the calculation of the percentage change from Baseline to Day 84.
- **Population level summary:** The difference in LS mean percentage change in LDL-C from Baseline to Day 84 between treatment groups

The analysis of covariance (ANCOVA) model with a fixed effect for the treatment group and covariates of Baseline LDL-C, CV risk (HeFH or non-HeFH), and Baseline statin therapy (HIS or non-HIS) will be used to analyze the primary efficacy endpoint. The CV risk and Baseline statin therapy covariates, that were used in the stratification of the randomization scheme, will be classified according to the IRT stratification levels (meaning, the stratification categorization at the time of the randomization). The least squares (LS) mean, standard errors, and 2-sided 95% confidence intervals for each treatment group and for the mean difference compared to placebo will be estimated. The model will be fit assuming unequal variances for each treatment group. If substantial deviations from the model assumptions are observed, then supportive analyses, such as non-parametric assessments, will be considered. The primary efficacy analysis will be conducted based on the ITT Population.

Missing data will be imputed for the primary efficacy analysis based on a pattern mixture model that uses a multiple imputation technique analyzed with ANCOVA with pre-specified fixed factors and covariates. If appropriate, based on the number of retrieved dropouts, missing measurements of non-retrieved dropouts will be modeled by known measurements from retrieved dropouts (ie, participants who remain in the study after treatment discontinuation) in the same treatment group. If the number of retrieved dropouts is such that the model convergence is questionable and the

given parameter estimates cannot be obtained, then missing data at the Day 84 assessment will be estimated based on the placebo treatment group as described in subsequent sections of the SAP corresponding to the first sensitivity analysis.

Missing data at Day 84 will be imputed using a retrieved dropout imputation model assuming the data are missing not at random (MNAR). At Day 84, the data will be split into two groups as follows: (1) all participants that did not discontinue treatment and had a non-missing value at Day 84; and (2) either participants that had a missing value at Day 84, or participants that had discontinued treatment and had a non-missing value at Day 84. For the second group, 100 data sets will be imputed. The variables for the imputation model will consist of the LDL-C values from Baseline and Day 84, along with treatment group, CV risk (HeFH or non-HeFH) and Baseline statin therapy (HIS or non-HIS). Each data set will be combined with the first group to obtain 100 imputed data sets with no missing values at Day 84. For each imputation data set, the percent change from baseline to Day 84 will be analyzed using the ANCOVA model described above. The results of these 100 analyses will be combined to construct the treatment estimates using the parameter estimates and associated standard errors. Similarly, the difference of the adjusted treatment means (obicetrapib vs. placebo) will be presented with the associated standard error and two-sided 95% confidence interval. Randomly chosen seed numbers will be selected for the analysis and will be retained.

Sample SAS code is shown below:

1.1

```
*****
Note: Missing value imputation only using participant group (2): participants that had a
missing value at Day 84, or participants that had discontinued treatment and had a non-
missing value at Day 84
```

TREATMENT = 0 (Placebo), 1 (Obicetrapib)

LDLC_BASE = Baseline LDL_C value

LDLC_Day84 = LDL_C value at Day 84

CVRISK = 1 (HeFH), 0 (non-HeFH)

STATIN = 1 (HIS), 0 (non-HIS)

```
*****
proc mi data=LDL_C seed=8267356 n impute=100 out= LDL_C_IMP;
class TREATMENT CVRISK STATIN;
monotone method=reg;
var TREATMENT CVRISK STATIN LDLC_BASE LDLC_DAY84;
run;
```

1.2

```
*****
Note: LDL_C_IMP dataset must be merged with dataset containing participants from
group (1): participants that did not discontinue treatment and had a non-missing value at
Day 84.
```

Note: For each imputation dataset, the percentage change from Baseline to Day 84 will be analyzed using an ANCOVA approach with a fixed effect for the treatment group and covariates of Baseline LDL-C, CV risk (HeFH or non-HeFH), and Baseline statin therapy (HIS or non-HIS).

TREATMENT = 0 (Placebo), 1 (Obicetrapib)

BASE = Baseline LDL_C value

PCHG = Percent change from Baseline to Day 84

```
CVRISK = 1 (HeFH), 0 (non-HeFH)
STATIN = 1 (HIS), 0 (non-HIS)
*****
proc mixed data= TEMP;
  by _imputation_;
  class TREATMENT CVRISK STATIN;
  model PCHG = TREATMENT BASE CVRISK STATIN /ddfm=satterth solution cl;
  repeated / group=TREATMENT;
  lsmeans TREATMENT / cl diff;
run;
*****
1.3
*****
Note: MI Analyze to combine imputations.
*****
proc mianalyze parms(classvar=full)=mixLSM;
  class TREATMENT;
  modeleffects TREATMENT;
  ods output parameterestimates=mi_LSM;
run;
proc mianalyze parms(classvar=full)=mixDIFF;
  class TREATMENT;
  modeleffects TREATMENT;
  ods output parameterestimates=minus_mi_DIFF;
run;
*****
```

Sensitivity Analyses

The first sensitivity analysis will be performed imputing missing LDL-C values at Day 84 based on the assumption the data are MNAR using a control-based pattern mixture method. At Day 84, the data will be split into two groups as follows: (1) all participants randomized to the obicetrapib treatment group that had a non-missing value at Day 84; and (2) either participants randomized to the placebo treatment group, or participants that had a missing value at Day 84. For the second group, 100 data sets will be imputed. The variables for the imputation model will consist of the LDL-C values from Baseline and Day 84, along with CV risk (HeFH or non-HeFH) and Baseline statin therapy (HIS or non-HIS). In this manner, missing data at the Day 84 assessment will be estimated from the placebo treatment group. Each data set will be combined with the first group to obtain 100 imputed data sets with no missing values at Day 84. For each imputation data set, the percent change from baseline to Day 84 will be analyzed using the ANCOVA model described above. The results of these 100 analyses will be combined to construct the treatment estimates using the parameter estimates and associated standard errors. Similarly, the difference of the adjusted treatment means (obicetrapib vs. placebo) will be presented with the associated standard error and two-sided 95% confidence interval. Randomly chosen seed numbers will be selected for the analysis and will be retained.

The second sensitivity analysis will be performed using a tipping point approach in the following steps [6-7]. The same analysis method as specified for primary analysis will be applied when analyzing adjusted data generated under each plausible shift parameter:

1. The missing data will be imputed using multiple imputation assuming missing at random (MAR) with a shift parameter in each treatment group.

2. The multiple imputed data will be analyzed using a standard multiple imputation method combining rule (Rubin's Rule).
3. Step 1 and 2 will be repeated such that the shift parameter for each treatment group will be increased in the negative and /or positive direction by a certain amount in each step until the "tipping point" is reached (i.e., where statistical significance is lost). The more the tipping point diverges from the observed data, the more robust the conclusions from the primary analysis.

The third sensitivity analysis will be performed using the ANCOVA model from the primary analysis for the ITT Population using only observed cases with no imputation for missing data.

The fourth sensitivity analysis will be performed using the eCRF data for stratification variables. This analysis will be performed only if stratification variables at IRT and in the eCRF disagree for more than 10% of the randomized participants.

Supplemental Analyses

Supplemental analyses will be performed for the primary efficacy endpoint in order to assess any differences with the results from the primary analysis and investigate what effect, if any, protocol violations have on the trial results. In the first supplemental analysis, a mixed model for repeated measures (MMRM) approach will be utilized. The LDL-C values measured by preparative ultracentrifugation will be used. The analysis will include fixed effects for treatment group, visit, and treatment-by-visit interaction, along with covariates of the Baseline LDL-C value as a continuous covariate, CV risk (HeFH or non-HeFH), Baseline statin therapy (HIS or non-HIS). The restricted maximum likelihood estimation approach will be used with an unstructured covariance matrix. The LS mean, standard errors, and 2-sided 95% confidence intervals for the treatment group and for the comparison of the treatment group to the placebo group will be provided. The MMRM approach will include all available assessments of percent change in LDL-C from Day 1, Day 30, Day 84, Day 180, Day 270, and Day 365. The model assumes that the data are missing at random (MAR). If any data are missing, the model will use all information from the other time points to estimate the mean treatment difference at the given time point. No imputation of missing data will be performed. The analysis will be conducted for ITT Population.

The analysis will be implemented using SAS® Proc Mixed. The sample SAS code can be found below:

Note:

USUBJID = unique subject identifier
TREATMENT = 0 (Placebo), 1 (Obicetrapib)
VISIT = visit
LDLC_BASE = Baseline LDL_C value
PCHG = Percent change from Baseline
CVRISK = 1 (HeFH), 0 (non-HeFH)
STATIN = 1 (HIS), 0 (non-HIS)

```
proc mixed;
  class USUBJID TREATMENT VISIT CVRISK STATIN;
  model PCHG = TREATMENT LDLC_BASE CVRISK STATIN VISIT TREATMENT*VISIT / solution cl;
  Repeated VISIT / TYPE=UN sub=USUBJID;
  lsmeans VISIT*TREATMENT / cl diff;
```

run;

Additional supplementary analysis will be performed using the ANCOVA model from the primary analysis based on the FAS, MITT, MITT On Treatment, and PP populations. No imputation for missing data will be performed for the analysis.

Secondary Estimand

A secondary estimand will be assessed for the primary efficacy endpoint. The secondary estimand is defined by the following key attributes:

- **Treatment:** obicetrapib versus placebo
- **Target Population:** participants who are randomized into the study
- **Analysis Population:** The ITT Population
- **Intercurrent events:** treatment discontinuation, prohibited medication use
- **Analysis set and handling of intercurrent events:** A hypothetical strategy will be used. All available values of LDL-C at Baseline and Day 84 will be included in the calculation of the percentage change from Baseline to Day 84.
- **Population level summary:** The difference in LS mean percentage change in LDL-C from Baseline to Day 84 between treatment groups.

This hypothetical estimand represents the treatment effect of obicetrapib relative to placebo at Day 84 in the randomized participants had they remained on their randomized treatment for the entire planned treatment period. This estimand uses a hypothetical strategy to handle intercurrent events and is intended to provide an estimation of the achievable study treatment effect participants take the treatment as planned. The resulting missing values (corresponding to unobserved values or excluded values following study drug discontinuation or the use of prohibited medication) will be implicitly handled by using an MMRM approach under the assumption of missing at random. The model will be similar to the MMRM approach described previously for the supplemental analysis of the primary efficacy endpoint.

